3.10. Missing, Unused, and Spurious Data

There will be no substitutions made to accommodate missing data points. All data recorded on the case report form will be included in data listings that will accompany the clinical study report.

When tabulating AE data, partial start dates will be handled as follows:

- If the year, month, and day are all missing, then set the onset day to the date of the first dose.
- If the month and day are missing, and the year is:
 - the same as the year of first dose, then set the onset day as the first day of the month of the first dose;
 - earlier than the year of first dose, then set the onset day as December 31;
 - after the year of the first dose, then set the onset day as January 1.
- If only the day is missing, then
 - if the month/year is the same as the first dose, then set the onset day as the date of first dose;
 - if the month/year is earlier than the month/year of the first dose, then set the onset day as the last day of the month;
 - if the month/year is later than the month/year of the first dose, then set the onset day as the first day of the month.

Partial end dates will only be imputed if the year is non-missing:

- If the month and day are missing, and the year is the same as the year of the last dose then set the end day as the last day of the month of the first dose. Otherwise, set the end date as December 31.
- If only the day is missing, then set the end day as the last day of the month.

If the imputed start date is later than the imputed/non-imputed end date then set the imputed start date to the imputed/non-imputed end date.

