#### **9.3.3.1        Adverse Events**

Adverse events will be classified using the Medical Dictionary for Regulatory Activities (MedDRA) classification system and the severity of the toxicities will be graded according to the NCI CTCAE v 5.0. Adverse event data will be summarized separately for Parts 3 and 4 and also combined (Parts 3 and 4).

In all summaries, emphasis will be placed on TEAEs, namely, those with initial onset or those that worsen in severity after the first dose of MT-3724. Adverse events will be summarized by the frequency of subjects experiencing TEAEs corresponding to MedDRA System organ class and preferred term and by worst NCI CTCAE grade. Summaries will also be provided of treatment related TEAEs, namely, those judged by the investigator to be related or likely related to MT-3724.

Adverse events resulting in discontinuation of MT-3724 treatment or withdrawal from the study, Grade 3 or higher, SAEs, and deaths on-study will be tabulated.

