4.6.1. Adverse Events

Adverse events (AEs) will be coded according to MedDRA Version 17.0 using system organ class (SOC) and preferred terms. Adverse events will be graded using the CTCAE v4.03. In the summary tables, subjects may be counted under multiple SOC and PT, but for each SOC and PT

category, subjects are only counted once. If a patient has the same AE on multiple occasions, the worst severity grade (fatal > life threatening > severe > moderate > mild) recorded for the event will be summarized.

Pre-treatment adverse events

All AEs that occurred before the first administration of MT-3724 are considered to be pre-treatment AEs.

Pre-treatment AEs will be summarized using frequency tables for subject count by CTCAE grade and worst CTCAE grade. Separate summary tables will be provided for serious and non-serious events. By-subject listings of pre-treatment AEs will be provided separately for serious and non-serious events. Summary statistics and listings of pre-treatment AEs will be provided for the overall safety population.

Treatment-emergent adverse events

All AEs that have started or worsened after the first administration of MT-3724 up until the last study assessment visit are considered to be treatment-emergent adverse events (TEAEs).

For each TEAE, the investigator will assess the causal relationship to MT-3724 as related and unrelated, where related = possibly, probably or definitely related, and unrelated = unlikely or definitely not related.

TEAEs will be summarized by treatment group using frequency tables for subject count by CTCAE grade and worst CTCAE grade. Separate tables will be provided for non-serious TEAEs, serious TEAEs and all TEAEs (non-serious and serious combined). The following tables will be provided for each of the above categories:

- TEAEs by MedDRA and Worst CTCAE Grade
- TEAEs by MedDRA and Worst CTCAE Grade, Only Grade 3/4/5 Events
- Related TEAEs by MedDRA and Worst CTCAE Grade
- Related TEAEs by MedDRA and Worst CTCAE Grade, Only Grade 3/4/5 Events
- Common TEAEs (occurring in $\geq 10\%$ of subjects) by MedDRA and Worst CTCAE Grade – Only for the overall population and MTD expansion

The following additional tables will be provided for all TEAEs (non-serious and serious combined)

- TEAEs Leading to Permanent Discontinuation by MedDRA and Worst CTCAE Grade
- Related TEAEs Leading to Permanent Discontinuation by MedDRA and Worst CTCAE Grade
- TEAEs Leading to Dose Reduction by MedDRA and Worst CTCAE Grade

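### SAP 3.10 can date a year-only adverse event before first dose and end it before it starts; separately, protocol 9.3.3.1 defines related events in words that do not match its causality scale

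*SAP*

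**What the plan says.** **Dates (SAP, which is based on protocol v7.0 and the extension protocol, so Parts 1 and 2 and the extension).** SAP 3.10 gives these rules for partial AE dates:

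- Onset known only to the year, first branch: "the same as the year of first dose, then set the onset day as the first day of the month of the first dose".
- Onset, nothing known: "If the year, month, and day are all missing, then set the onset day to the date of the first dose".
- Onset, only the day missing: "if the month/year is the same as the first dose, then set the onset day as the date of first dose".
- End, month and day missing, year equal to the year of the last dose: "set the end day as the last day of the month of the first dose". Any other year-only end becomes 31 December.
- Order check: "If the imputed start date is later than the imputed/non-imputed end date then set the imputed start date to the imputed/non-imputed end date".

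SAP 4.6.1 uses the result to classify events: "All AEs that occurred before the first administration of MT-3724 are considered to be pre-treatment AEs". Events that started or worsened after first administration are TEAEs. Pre-treatment events are summarised for the overall safety population; TEAEs are summarised by treatment group. The related-event, dose-reduction, interruption and discontinuation tables, and the listings of DLTs and deaths, are all restricted to TEAEs.

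**Relatedness (protocol v11, Parts 3 and 4).** Section 9.3.3.1 defines treatment-related TEAEs as "those judged by the investigator to be related or likely related to MT-3724". Table 10-3 has five categories: definitely, probably and possibly related, unlikely, and unrelated. Section 10.3.5 groups the first three as related, for subject management, DLT assignment and treatment modification. SAP 4.6.1 uses the same grouping for its tables: "where related = possibly, probably or definitely related".

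**The concern.** The onset rules run against the amount of information. An event with no date at all is placed on the date of first dose. An event known to have begun in the year of first dose is placed at the start of that month, usually before dosing. The SAP gives no reason for the difference, and it reads as a drafting slip. An event moved this way loses its dose-cohort attribution and leaves the related-event tables, in a study whose purpose is to describe safety by dose.

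The end rule tests one dose and imputes from another: its condition concerns the last dose and its result the first. A later event can then end before it began, and the order check repairs only imputed starts, not recorded ones.

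The relatedness wording is a separate matter, in another document and for other study parts. It leaves open whether possibly related events belong in the treatment-related table for Parts 3 and 4.

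**Working it through.** The documents give no figure to reproduce, so the rules were applied literally.

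**1. Onset rule.** Let F be the date of first dose and d its day of the month. The imputed onset is O = F − (d − 1) days, so O < F whenever d > 1. Assume F is equally likely to be any day of a 365-day year.

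- Dates giving a pre-dose onset: 365 − 12 = 353; 353/365 = 96.7%. Restricted to the weekdays of 2018 the count is 253 of 261 (96.9%).
- Mean shift: Σ(d − 1)/365 = (7 × 465 + 4 × 435 + 378)/365 = 5373/365 = 14.7 days, range 0 to 30.

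Example, first dose 20 March 2018:

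| What is recorded for onset | Imputed onset | Class by date |
|---|---|---|
| Nothing | 20 March | TEAE |
| March 2018 | 20 March | TEAE |
| 2018 | 1 March | Pre-treatment |

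This takes an onset on the date of first dose as treatment-emergent, as the neighbouring rules evidently intend. With the date of first dose used in the third row as well, 0 of 365 dates give a pre-dose onset.

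**2. End rule.** The imputed end E is the last day of the month containing F, so E ≥ F always. If the order check pulls an imputed start back to E, that start is still on or after first dose. The rule therefore never turns a TEAE into a pre-treatment event.

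Example: first dose 20 March 2018 and five 21-day cycles with the last dose on Day 12. The last dose is 21 × 4 + 11 = 95 days later, 23 June. An event with recorded onset 15 May and end 2018 gets an end of 31 March, 30 + 15 = 45 days before it began. If the onset were recorded only as May 2018 (imputed to 1 May), the order check would move it to 31 March and override a recorded month.

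Frequency, assuming 1 to 5 cycles of 21 days, first and last dose in the same calendar year, and recorded onset equally likely on any day of that year from first dose to 14 days after last dose:

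| Cycles | Imputed end precedes onset, current rule | Same, using month of last dose |
|---|---|---|
| 1 | 39% | 13% |
| 2 | 66% | 7% |
| 3 | 76% | 5% |
| 4 | 82% | 4% |
| 5 | 86% | 3% |

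A floor at the onset date takes the last column to 0. The 28-day first cycle of Part 1, the extension cycles and dosing across two calendar years are not in this table; in the last case the rule does not say which year the imputed month belongs to.

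**3. Relatedness wording.** Neither term in 9.3.3.1 is a Table 10-3 category, and two readings are open:

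- Related means the 10.3.5 group. Possibly related events are then counted, and the added words about likely related events are redundant.
- Related means definitely and likely means probably. Possibly related events are then left out.

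Section 10.3.5 does not name tabulation among its purposes, and the SAP supplied does not cover Parts 3 and 4, so neither settles it.

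**The case against.** The strongest reply is that little is lost in practice.

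- Misdated events are not deleted. They appear in the pre-treatment tables and listings, with serious events shown separately, and an event that worsened after first dose is still a TEAE. This stands: a reader might infer that the rules drop drug events from the safety tables, but the fault is misclassification.
- A reader might also infer that both date rules under-count TEAEs. The end rule cannot, as shown above. Nor does any table or listing named in SAP 4.6.1 report AE duration, so its harm lies in the derived dates.
- Year-only onsets should be uncommon during treatment, because AEs are reviewed at every dosing visit. The six-monthly follow-up calls are a likelier source. This is plausible, but the documents give no count.
- The 96.7% applies only to events with a year-only onset in the year of first dose. It is not a share of all AEs.
- On relatedness, the word related can naturally carry its 10.3.5 meaning, and the protocol defers detailed methods for Parts 3 and 4 to a SAP that is not among the documents. The inference that every possibly related event leaves the related table is therefore one reading, not an established omission.

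None of this supplies a reason for the onset rule to differ from its neighbours, or for the end rule to refer to the first dose.

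**Conclusion.** The two date rules in SAP 3.10 are wrong as written. The onset rule places a year-only event before first dose for 353 of 365 first-dose dates, 14.7 days early on average, and SAP 4.6.1 then takes it out of the by-cohort TEAE and related-TEAE tables unless it worsened after first dose. The end rule can put an end before a recorded onset, or pull a partly known onset back to the month of first dose, but it removes no TEAE. Only year-only dates are affected. Their number is not given, so the effect on AE counts is unknown. The percentages rest on uniformly distributed first-dose dates and, for the end rule, on the schedule assumed above.

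Protocol 9.3.3.1 is ambiguous rather than demonstrably wrong. On any reading, possibly related events stay in the all-TEAE tables, and in the Grade 3 or higher, SAE and discontinuation tables where they qualify.

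It is tempting to add the problems together and tie them to the fatal capillary leak syndrome event. The documents do not support that. The date rules govern Parts 1 and 2 and the extension, while the relatedness wording governs Parts 3 and 4. The SAP itself counts possibly related events as related, so the faults do not meet in one table. The Grade 5 event occurred in Part 3, outside the reach of these SAP rules.

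**What to change.** - **SAP 3.10, onset.** For a year-only onset in the year of first dose, impute the date of first dose, unless a known end date is earlier. The existing order check already handles that exception.
- **SAP 3.10, end.** For a year-only end in the year of last dose, impute the last day of the month of the last dose. If that falls before onset, set the end to the onset date. Keep the order check that moves an imputed start for cases where the end date is recorded.
- **Protocol 9.3.3.1.** State that related means definitely, probably or possibly related, as in 10.3.5 and SAP 4.6.1.

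Reporting how many AE dates were imputed under each rule would show whether any of this changed a table.

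The cost is three sentences and a small programming update, with no new data. Reported related-event rates in Parts 3 and 4 may be somewhat higher than under the narrower reading.

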3.11. Visit Windows

It is expected that all visits should occur according to the protocol schedule. All data will be tabulated per the evaluation visit as recorded on the eCRF even if the assessment is outside of the visit window. In data listings, the relative day of all dates will be presented.

3.12. Interim Analyses

There are no planned formal interim statistical analyses of the data. Interim safety data will be examined on an ongoing basis to ensure subject safety and to comply with the clinical trial dose escalation rules. Interim efficacy data may be examined on an ad hoc basis.

4. STUDY ANALYSES

All analyses will be presented by the following MT-3724 treatment groups:

- Cohort 1 (5 mcg/kg/dose)
- Cohort 2 (10 mcg/kg/dose)
- Cohort 3 (20 mcg/kg/dose)
- Cohort 4 (50 mcg/kg/dose)
- Cohort 5 (100 mcg/kg/dose)
- Cohort 6 (75 mcg/kg/dose)
- Cohort 7 / MTD Expansion Cohort (50 mcg/kg/dose)
 - Although 3 subjects enrolled in the original MTD of 75 mcg/kg/dose in Cohort 7, only those enrolled at a starting dose of 50 mcg/kg will be considered for the purpose of analysis
- A cohort which combines all patients with a starting dose of 75 mcg/kg, hereafter referred to as the 'Combined 75 mcg/kg/dose' Cohort
- A cohort which combines all patients with a starting dose of 50 mcg/kg, hereafter referred to as the 'Combined 50 mcg/kg/dose' Cohort

In addition, overall tabulations will be presented in appropriate analyses.

All analyses will be performed on integrated Main and Extension studies.

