1.2.1. Main Study

1.2.1.1. Primary Objectives

In Part 1, subjects with NHL or CLL were enrolled, and the primary objectives were:

- To define the maximum tolerated dose (MTD) of a single course of MT-3724 given on Days 1, 3, 5, 8, 10 and 12 at which there are negligible side effects (adverse events) and/or at which maximum pharmacokinetic (PK)/pharmacodynamic (PDn) parameter changes are observed.
 - The MTD was determined to be 75 mcg/kg/dose. However, due to safety concerns, an adjusted MTD (50 mcg/kg/dose) is used for Part 2.
- To determine PK and PDn profiles of a single course of MT-3724 in escalating dose cohorts.

In Part 2, up to 40 additional subjects with relapsed/refractory diffuse large B-cell lymphoma (DLBCL) will be treated with the adjusted MTD (50 mcg/kg/dose) of MT-3724 in the MTD expansion cohort. The primary objectives will be to:

- Identify the frequency and nature of clinical and laboratory adverse events (AEs), both reported and observed, as a measure of safety and tolerability over repeated cycles of MT-3724 at the adjusted MTD.
- Define the PK and PD profiles of MT-3724 at the adjusted MTD in this sub-population.

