1.3.1.2. Extension Study

This is an active treatment, extended access study open solely to those subjects who have successfully completed the Core and Repeat Dosing portions of the MT-3724_NHL_001_US

clinical study and who, in the Investigator's judgment (i) have not had progressive disease while on MT-3724 treatment (i.e., have shown a complete or partial response or stable disease), (ii) have experienced no clinical or laboratory toxicities that would contraindicate further MT-3724 dosing, and (iii) have no acceptable and better alternative treatment available to them. Each treatment cycle will consist of 6 doses of MT-3724 to be administered over 12 days followed by at least 9 days of observation; longer intervals between dosing cycles will be allowed at the Investigator's discretion (e.g., 6 doses of MT-3724 over 12 days followed by 16 days observation). Subjects in this extension study may continue to receive up to 6 additional cycles in the absence of clear disease progression or toxicity. If a subject achieves complete remission (CR), two additional cycles will be attempted, after which dosing may be suspended prior to completion of the maximum 6 cycles.

A schematic of the extension study is presented in Figure 3, and schedule of assessments are provided in Table 3.

Figure 3: Extended Access Schematic

Dosing Cycles

As in the MT-3724_NHL_001_US Repeat Dosing Study each subject will continue to receive six (6) MT-3724 intravenous (IV) infusions over approximately 12 days (Days 1, 3, 5, 8, 10 and 12) followed by at least 9 days observation (Days 13 – 21) observation for a maximum of 6 cycles. At the Investigator's discretion the observation period between treatment periods may be extended to 16 days for one or more cycles following discussion with the Sponsor. Each subject may continue to receive the same dose (mcg/kg) which they had been receiving in the Repeat Dosing Study OR, in consultation with the Sponsor, a subject may be reassigned to receive the maximum tolerated dose (MTD) identified in the MT-3724_NHL_001_US Core Study. If a

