subject enrolls in this study prior to the identification of the MTD in the Core Study, the subject must continue at their originally assigned dose (mcg/kg) until the MTD is identified. If a subject has tolerated repeat cycles of MT-3724 without evidence of (i) a toxicity that would prohibit further dosing or (ii) disease progression, but their dose is subsequently determined to be above the MTD, they may continue to receive additional cycles at the highest studied dose that has been confirmed to be below the MTD or at the dose confirmed to be the MTD. Following the successful completion of a treatment cycle in this extended access study, subjects are eligible to receive the next cycle (to a maximum of 6 cycles) as long as (i) they have experienced no AE attributable to MT-3724 which contraindicates further dosing AND (ii) their disease has not progressed. For subjects in any dosing cohort who complete less than 4 of the 6 infusions in a cycle, and the missed infusions were not due to an MT-3724 related AE that would contraindicate further dosing then the Investigator may attempt to achieve a minimum of 4 infusions by administering the missed doses in the third week of that dosing cycle. In such an instance, for that cycle only, at the Investigator's discretion and in consultation with the Medical Monitor, a subject may be observed for less than 9 days prior to initiating their next cycle.

Long Term Safety Follow-up (Extension)

Following the assessment performed 14 - 28 days after the last MT-3724 dose in this study, subjects will be contacted by telephone every 6 months from the date of their first dose in the MT-3724_NHL_001_US Core Study for up to 2 years OR until they initiate further treatment for their B-cell Non-Hodgkin's Lymphoma (NHL) or B-cell Chronic Lymphocytic Leukemia (CLL) OR until they take any other investigational new drug for any reason. During these telephone contacts subjects will be asked about their current medical status and if they have experienced any new AE attributable to their MT-3724 treatment.

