		Visit 2 Day 1 Dose 1	Visit 3 Day 3 Dose 2	Visit 4 Day 5 Dose 3	Visit 5 Day 8 Dose 4	Visit 6 Day 10 Dose 5	Visit 7 Day 12 Dose 6	Day 16-25			
12-Lead ECG ¹⁰	X (only when clinically indicated)										
Cancer Histology	X (Confirm history) X (repeat only when clinically indicated)										

Abbreviations: ADA: anti-drug antibodies; ALT: alanine aminotransferase; AST: aspartate aminotransferase; BUN: blood urea nitrogen; Ca: calcium; CBC: complete blood count; Cl: chloride; CO₂: carbon dioxide; CPK: creatine phosphokinase; Cr: creatinine; CT: computed tomography; ECG: electrocardiogram; ECOG: Eastern Cooperative Oncology Group; GGT: gamma-glutamyl transferase; HepBAb: hepatitis B antibody; HepBAg: hepatitis B surface antigen; HepCAb: hepatitis C antibody; HIV: human immunodeficiency virus; IFN- γ : interferon gamma; IL-6: interleukin 6; K: potassium; LDH: lactate dehydrogenase; Mg: magnesium; MRD: minimal residual disease; NA: sodium; PET: positron emission tomography; PK: pharmacokinetic; TNF α tumor necrosis factor alpha

¹ Height and weight are collected at the Screening Visit. Weight is collected again at Final Safety Visit 14-28 days after last infusion. MT-3724 dose is re-calculated using Screening Visit weight if subject's weight has changed by $\pm 10\%$ from MT-3724_NHL_001_US study, the dose OR subject's mcg/kg/dose must be changed due to MTD identification.

² See Protocol Appendix 3. CT scans will be performed for tumor assessment at screening and Final Safety Visit. Additional tumor assessment (s) will be performed per investigator. Where clinically indicated, PET scan may also be performed per Investigator discretion.

³ For all infusions, all cycles, vital signs (temperature, blood pressure, pulse, and respiration rate) should be collected prior to the initiation of the infusion and at the conclusion of the infusion. Beyond these times subjects should be monitored as clinically indicated. The frequency of interim monitoring during and following all infusions should be determined by the Investigator based on the subject's clinical condition. In addition, in all subjects, orthostatic vital signs will be performed as needed after all doses prior to the subject standing or ambulating for any reason during the observation period

⁴ Calculate estimated creatinine clearance by Cockcroft Gault formula.

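### By-cohort toxicity and laboratory tables pool Main and Extension data and do not separate what is seen after a subject is reassigned to another dose

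*SAP*

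**What the plan says.** SAP section 4 opens with "All analyses will be presented by the following MT-3724 treatment groups". The groups are six Part 1 cohorts (5, 10, 20, 50, 100 and 75 mcg/kg), the Part 2 expansion (Cohort 7, 50 mcg/kg), and two groups combining everyone who started at 75 or at 50. For Cohort 7, "only those enrolled at a starting dose of 50 mcg/kg will be considered for the purpose of analysis", so group membership, where the SAP states a basis, follows starting dose. The section closes with "All analyses will be performed on integrated Main and Extension studies".

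SAP section 1.3.1.2 describes dosing in the Extension. A subject may keep the dose from Repeat Dosing, or "in consultation with the Sponsor, a subject may be reassigned to receive the maximum tolerated dose (MTD) identified in the MT-3724_NHL_001_US Core Study". A subject whose dose turns out to be above the MTD may go on at "the highest studied dose that has been confirmed to be below the MTD or at the dose confirmed to be the MTD". Anyone who enrols before the MTD is known stays on the original dose until it is. On duration: "Subjects in this extension study may continue to receive up to 6 additional cycles in the absence of clear disease progression or toxicity". Table 3, footnote 1 (section 1.3.4) allows for the case where the subject's "mcg/kg/dose must be changed due to MTD identification". On the MTD itself, section 1.2.1.1 says: "The MTD was determined to be 75 mcg/kg/dose. However, due to safety concerns, an adjusted MTD (50 mcg/kg/dose) is used for Part 2".

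For tabulation, section 4.6.1 counts TEAEs from the first dose to the last study assessment visit, by treatment group, at worst grade. Section 4.6.2 tabulates laboratory shifts from baseline to worst value. Section 3.4 sets one baseline for both studies, before the first Main Study dose.

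**The concern.** These tables are the descriptive dose-toxicity output of a dose-finding study, and a reader takes the column heading as the dose that produced the events. The SAP foresees a change of dose within a column but does not cut the data at that point or show events by dose received. A Grade 3 event at 50 or 75 mcg/kg could therefore appear under 5, 10 or 20 mcg/kg and make a low dose look more toxic than it was. In the other direction, an event after a move down from 100 mcg/kg would still be shown under 100.

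The Extension also has its own primary objective of describing adverse events over cycles beyond those in the Main Study (section 1.2.2.1). With everything integrated, no planned table isolates those cycles.

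**Working it through.** The plan gives no figure on this point to reproduce. The check is a reading of the SAP for an attribution rule, plus simple arithmetic for scale.

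**1. Is there a rule?**
- Section 4: groups and integration only. There is no split at a dose change and no Main-only or Extension-only table.
- Section 4.6.1, TEAE tables: the window runs from first dose to last visit, with no reference to dose at onset.
- Section 4.6.1, listings: preferred term, worst grade, relatedness, outcome and seriousness. Dose is not included.
- Section 4.6.2 with section 3.4: the worst value can come from any cycle, and the baseline is not reset.
- Section 4.5: summaries of total drug, number of doses, dose intensity and dose reductions, and a by-subject dosing listing. Dose increases are not counted.
- Section 4.3: part of the text is not visible. The endpoint definitions in section 1.3.5.2 contain no split at a dose change, but a rule in the hidden text cannot be excluded.

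For TEAEs and laboratory shifts, no summary table separates data after a move.

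**2. How large is the dose change?** The ratio is MTD divided by cohort dose. The SAP gives both 75 and an adjusted 50, so both are shown.

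| Cohort dose (mcg/kg) | MTD 75 | MTD 50 |
|---|---|---|
| 5 | 15 | 10 |
| 10 | 7.5 | 5 |
| 20 | 3.75 | 2.5 |
| 50 | 1.5 | 1 |
| 100 | 0.75 | 0.5 |

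For 5, 10 and 20 mcg/kg the move is upward under either reading.

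**3. What does one subject do to a rate?** Planned cohort size is 3 to 6 (section 1.3.1.1). One subject with a new or worse event after the move adds 1/6 = 16.7 points or 1/3 = 33.3 points. Cohorts could be enlarged, and the combined groups may be larger, so the shift there would be smaller.

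**4. How much exposure could be at the new dose?**
- Theoretical ceiling: the Main Study gives 5 × 6 = 30 doses and the Extension 6 × 6 = 36, so 36/66 = 54.5%. This needs all 11 cycles and a move at the first Extension dose.
- Protocol section 12.3 (Version 9 rationale) reports exposure for up to 9 cycles. Five Main plus four Extension cycles gives 24/54 = 44.4% at most.
- The rule holding early enrollees at their original dose lowers this further for the first cohorts. As an illustration, assume instant enrolment, no gaps, and the MTD identified when the sixth cohort completes its 28-day Core period: 6 × 28 = 168 days. A Cohort 1 subject finishes Main dosing at 28 + 4 × 21 = 112 days. The remaining 56 days cover the start of three 21-day Extension cycles, all at 5 mcg/kg. At most 3 × 6 = 18 of 66 doses (27.3%) could then be at the new level. Slow enrolment tightens this and treatment gaps loosen it.

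**The case against.** The strongest reply is that grouping by starting dose is a usual convention, and that the SAP does attribute later data: to the original cohort. That stands as a defence of the main display. It settles who belongs in a column, but it does not show which events in the column arose at another dose.

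A second reply is that the information already exists. Section 4.5 summarises total drug and dose counts and lists dosing, section 4.1 counts subjects continuing into the Extension, and section 3.2 puts relative study day in dated listings. A reader could match onset to dose by hand. That is true, and it limits the harm, but the summary tables would still mix doses. Only cumulative or worst-value tables are exposed. Laboratory summaries by scheduled time point, and vital-sign changes within a visit, are much less so.

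Third, the effect is conditional. Reassignment was optional, Extension entry required no progression and no toxicity that would contraindicate further dosing, and the event must be new or worse after the move. All of this stands. Extension protocol v2.0 was not supplied, so the SAP's own account is the only source here.

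Three stronger readings are tempting, and the documents do not support them:
- **That the MTD finding is contaminated.** Section 1.3.5.1 limits dose-limiting toxicities to the Core Study.
- **That more than half of a subject's exposure was at the wrong label.** The 54.5% is a ceiling that the holding rule and the reported 9 cycles make unlikely, above all for the lowest cohorts.
- **That response rates are shown to be misattributed.** The concern may extend to response, but section 4.3 cannot be read in full, and efficacy in this SAP is exploratory.

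**Conclusion.** The point holds for the TEAE and worst-value laboratory tables by cohort. If any Extension subject was reassigned, events that first appeared or worsened afterwards would be counted under the original cohort's dose, and no planned summary table would separate them. One such subject shifts the rate by 16.7 to 33.3 points in a cohort of 3 to 6. For response, the question stays open.

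The conclusion rests on the SAP's description of the Extension, on planned rather than actual cohort sizes, and on at least one subject having changed dose, which the documents do not establish. If none did, no table changes. The analyses are descriptive and cover Parts 1 and 2 with the Extension. The Part 4 hypothesis test in the protocol is not touched. This is a worthwhile, low-cost improvement rather than a flaw in the dose-finding result.

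**What to change.** In SAP section 4, keep the integrated starting-dose tables as the main display and do not truncate them. Then:

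1. Add one supplementary TEAE and laboratory-shift display. It cuts each subject's data at the first dose at a reassigned level and shows later data by dose level received, with the number of subjects and cycles at that level. The same cut should apply to the downward move that section 1.3.1.1 allows in Part 1 Repeat Dosing.
2. Add a column to the TEAE listings in section 4.6.1 for the last dose received before onset.
3. State whether the MTD for Extension reassignment means 75 or the adjusted 50 mcg/kg, and how many subjects were reassigned. If none were, one sentence in section 4 replaces items 1 and 2.

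The cost is one extra table with small denominators and one listing column. Both draw on dosing data already planned for listing under section 4.5, with no new data collection and no change to dosing.
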